Understanding whether cognition, in middle aged and older healthy adults, may be positively affected by the oral consumption of postbiotics, is important for helping us better understand the neuroprotective and enhancing properties of postbiotics and their future implementation into food and supplements. Electroencephalography (EEG) is a low cost, non-invasive method to record an electrogram of the spontaneous electrical activity of the brain. The bio signals detected by EEG have been shown to represent the postsynaptic potentials of pyramidal neurons in the neocortex and allocortex. It shall be combined with 3 psychological tasks (Stroop, Go/No-Go, and Flanker), to measure a variety of cognitive domains including attention, processing speed, accuracy, and response inhibition (Davidson et al., 2003; Feil et al., 2003; Redick et al., 2011). An eyes open/closed task will obtain baseline measurements for resting state. The Mini Mental State Exam (MMSE) questionnaire and geriatric depression scale (GDS) shall be used as screening tools to assess global cognitive function and depressive symptomology in participants prior to taking part. The EQ-5D questionnaire shall be used to obtain an overall profile of the health state and quality of life of participants.

We will collect venous blood samples (3 x 4.5mL) for the investigation into the chemical composition using metabolomics at AberInnovation and Aberystwyth University, the quantification of short box chain fatty acids as well as clinical biochemistry (Chem21 to include lipid panel tests) at Bronglais hospital.

2) Statement of Purpose

A randomised, placebo controlled parallel human clinical trial of heat-treated *Lactobacillus paracasei* (post-biotics) in healthy middle aged and older subjects is proposed, to assess the potential for clinically relevant benefits in terms of cognitive function. We are aiming to recruit a cohort (n = 30) of middle aged and older adults (>50 years) who will be randomised into PoZibio™ (2 x capsules daily) or placebo (2 x capsules daily) supplementation for 6 weeks. Subjects will be asked to take both capsules in the morning with their breakfast. The placebo will be matched to the active product by taste and texture.

3) Investigational Product

3.1) Description

The investigational product will contain a capsule with heat-treated *Lactobacillus paracasei* (inactivated cells count 50 billion counts (50×10^9 CFUs/ capsule)). The format will be a

GDPR: For the data the Welsh Government requires, Welsh Government is the data controller and Aberystwyth University (WARU) is the data processor. For any other data, including sensitive personal data, the data controller and the data processor is Aberystwyth University (WARU).

167 mg capsule bottle containing the 2 capsules daily. The placebo will be matched to the active product by taste and texture.

60 capsules. Subjects will be asked to take

3.2) Quality

This product is free of the following components and their products thereof: cereals containing gluten, crustaceans, eggs, fish, peanuts, soybeans, milk (including lactose), nuts, celery, mustard, sesame seeds, sulphur dioxide and sulphite, lupin and molluscs, in compliance with Regulation (EC) No. 1169/2011. This product does not contain added colorants. Cultures are Kosher, Halah approved. The supplements are vegan, and they are produced and stored in a food grade facility. The freeze-dried culture is packaged inside waterproof and airproof pouches, consisting of three layers (in order, going inwards): polyester, aluminium, and polyethylene. The packaging material used is food grade.

3.3) Dose

The dose of investigational product and placebo will be 2 x 1 ml capsules daily.

4) Investigational Product Safety

The species *Lactobacillus paracasei* is included in EFSA's Quality Presumption of Safety (QPS) list. Total inactivated cells count > 1.5E+11 cells/g. The microbial strains are not genetically modified (GMO), in accordance to the European Directive 2001/18/EC. This product is not hazardous. Sacco S.r.l. is ISO 22000 and FSSC 22000 (food safety) certified since 2014. This product is considered safe with respect to bovine spongiform encephalopathy (BSE) or transmissible spongiform encephalopathies (TSEs) transmissions in accordance to Regulation EMA 410/01 rev. 3.

5) Study Design

5.1) Objectives of the Study

5.1.1) Primary Outcome Measure:

- Cognitive Control (Selective attention, processing speed, mental flexibility)

Cognitive Control (Selective attention, processing speed, mental flexibility) measured using the Stroop task in E-Prime

[Time Frame: Improved score (faster response time and improved accuracy) from baseline score at 6 weeks after pozibio]

- Cognitive Control (Selective attention, processing speed, mental flexibility)

Cognitive Control (Selective attention, processing speed, mental flexibility) measured using the Stroop task in E-Prime

EuroQol 5 Dimension 5 5L questionnaire: Generic quality of life. Mobility- Level 1-5 Self-Care- Level 1-5, Usual Activities- Level 1-5, Pain/Discomfort- Level 1-5, Anxiety/Depression- Level 1-5, EQ-VAS: Numerical value between 0-100 representing how the patient perceives their overall health to be.

[Time Frame: Reduced EuroQol 5 Dimension 5 score at 6 weeks after pozibio when compared with placebo after 6 weeks]

5.1.2) Secondary Outcome Measures:

- C-reactive protein

C-reactive protein in plasma as a marker of inflammation

[Time Frame: Reduced C-reactive protein from baseline at 6 weeks after pozibio]

- C-reactive protein

C-reactive protein in plasma as a marker of inflammation

[Time Frame: Reduced C-reactive protein at 6 weeks after pozibio when compared with placebo after 6 weeks]

- Kidney function tests

Kidney function tests including sodium/potassium/creatinine/urea

[Time Frame: Reduced Kidney function tests from baseline at 6 weeks after pozibio]

- Kidney function tests

Kidney function tests including sodium/potassium/creatinine/urea

[Time Frame: Reduced Kidney function tests at 6 weeks after pozibio when compared with placebo after 6 weeks]

GDPR: For the data the Welsh Government requires, Welsh Government is the data controller and Aberystwyth University (WARU) is the data processor. For any other data, including sensitive personal data, the data controller and the data processor is Aberystwyth University (WARU).

➤ Total Cholesterol

Total Cholesterol

[Time Frame: Reduced total Cholesterol from baseline at 6 weeks after pozibio]

➤ Total Cholesterol

Total Cholesterol

[Time Frame: Reduced total Cholesterol at 6 weeks after pozibio when compared with placebo after 6 weeks]

➤ Total Triglyceride

Total Triglyceride

[Time Frame: Reduced total Triglyceride from baseline at 6 weeks after pozibio]

➤ Total Triglyceride

Total Triglyceride

[Time Frame: Reduced total Triglyceride at 6 weeks after pozibio when compared with placebo after 6 weeks]

➤ Liver function tests (LFTs)

Aspartate aminotransferase (AST), Alanine transaminase (ALT), Alkaline phosphatase (ALP), Gamma-glutamyltransferase (GGT), Prothrombin time (PT), Albumin,
[Time Frame: Reduced Liver function test from baseline at 6 weeks after pozibio]

➤ Liver function tests (LFTs)

Aspartate aminotransferase (AST), Alanine transaminase (ALT), Alkaline phosphatase (ALP), Gamma-glutamyltransferase (GGT), Prothrombin time (PT), Albumin,
[Time Frame: Reduced Liver function test results at 6 weeks after pozibio when compared with placebo after 6 weeks]

➤ Changes in short chain fatty acids concentrations in plasma

Changes in short chain fatty acids concentrations in plasma measured using Gas Chromatography-Flame Ionization Detection

[Time Frame: Increased concentration of total short chain fatty acids after the pozibio at 6 weeks compared with the baseline]

➤ Changes in short chain fatty acids concentrations in plasma

Changes in short chain fatty acids concentrations in plasma measured using Gas Chromatography-Flame Ionization Detection

[Time Frame: Increased concentration of total short chain fatty acids after the pozibio at 6 weeks compared with that after placebo at 6 weeks]

5.2) Subject Selection

GDPR: For the data the Welsh Government requires, Welsh Government is the data controller and Aberystwyth University (WARU) is the data processor. For any other data, including sensitive personal data, the data controller and the data processor is Aberystwyth University (WARU).

- 30 participants, over 50

years, mixed gender, mixed ethnicity.

- **Inclusion Criteria:**

- Subjects over 50 years of age.
- Subjects with Mini-Mental State Exam (MMSE) of 25-30 inclusive (global cognitive function). Subjects who are able to undergo EEG and to commit to visits to WARU/P5.
- Subjects who are able to provide venous blood samples.
- Subjects able to provide written informed consent PRIOR to performing any study procedures.

- **Exclusion Criteria:**

- Subjects with diagnosis of Alzheimer's disease or other dementia.
- Subjects taking medication for the treatment of dementia (such as acetylcholinesterase inhibitors (Aricept, Exelon), memantine (Namenda) or other medications with similar mechanisms of action) or medical foods (such as Cerefolin, Souvenaid, Axona) for the treatment of dementia.
- Subjects who are already regularly taking probiotics, post-biotics, nutraceutical and/or vitamin supplements related to *PoZibio*™ within 30 days of screening.
- Subjects with Geriatric Depression Scale > 6.
- Subjects with a Mini Mental State Exam score below 25.
- Subjects who are pregnant or lactating.
- Subjects with medical condition or disease that is life threatening.
- Subjects who smoke cigarettes or use other products containing nicotine.
- Subjects diagnosed with diabetes.
- Subjects taking warfarin.
- Subjects who have a diagnosed or suspected mental health condition, or who have any concerns surrounding their mental health.
- Subjects who have immediate family members with diagnosed mental health condition or suspected mental health concerns.

- **Covid Exclusion criteria**

- Showing (or anyone within the household) any COVID-19 symptoms (see COVID-19 basic health screen)*
- Higher risk or vulnerable from coronavirus or live with someone at a higher risk of a severe illness from COVID-19 (over 70, undergoing cancer treatment, high risk of getting infections).
- Had a letter from the NHS advising you to shield (isolate).

- Had been at risk of exposure to COVID-19 such as travel, contact with someone with COVID-19, been exposed to the virus, or has been asked to self-isolate by the track and trace system.
- Serious health conditions that require daily long-term medication.

*If the potential participant has had COVID-19 previously (and are fully recovered and not within isolation) then they are eligible to join the study.

5.3) Study Design

This is a randomised, placebo controlled, parallel study, where participants are asked to take the capsules (PoZibio™ or Placebo) twice a day for a period of 6 weeks. Participants will be required to make five visits to the Well-being and Health Assessment Research Unit (WARU) and Psychology department at Aberystwyth University; however, several visits can be combined if needed. EEG data analysis will be conducted at Aberystwyth University. Chemical composition using metabolomics will be conducted at AberInnovation and Aberystwyth University, and the quantification of short chain fatty acids as well as clinical biochemistry (Chem21 to include lipid panel tests) will be analysed at Bronglais hospital.

Pre-Induction

Participants are welcomed with tea or coffee and talked through how safe working practices are being conducted during coronavirus (COVID-19). Participants are informed that they will be completing the Mini Mental State Exam (MMSE) to assess their overall cognitive function, and the Geriatric Depression Scale (GDS) to assess for any depressive symptomatology, as part of the screening process. They are reminded that these screening questionnaires are not diagnostic and are not intended for clinical assessment purposes; instead, they are to ensure consistency across the participant sample, whereby the inclusion and exclusion scores are taken from pre-existing literature. Participants are informed that the MMSE should take approximately 10 minutes to complete, and the GDS will take approximately 5 minutes to complete, and that they will be told their scores after they have completed both questionnaires. If they meet the:

- **Inclusion Criteria:**
Their scores will be retained, but their name will be pseudonymised using their randomised, unique code, and only the researchers closely affiliated with the project will have access to their data
- **Exclusion criteria:**
They will no longer be able to continue with the study, their data will be deleted, and they shall be provided a participant exclusion form with what to do next.

Participants are provided with the chance to ask any questions. If they are happy to continue, they are asked to read and sign the consent form. After screening ends, participants are offered water and the opportunity to use the bathroom whilst their scores are calculated.

If they meet the inclusion criteria, then:

- A record of their scores is retained in an excel spreadsheet next to their anonymous ID code.
- They are informed that they have met the inclusion criteria.

GDPR: For the data the Welsh Government requires, Welsh Government is the data controller and Aberystwyth University (WARU) is the data processor. For any other data, including sensitive personal data, the data controller and the data processor is Aberystwyth University (WARU).

- They are thanked for their

time and walked to the door.

If they do not meet the inclusion criteria, then:

- A note of their scores is made in the participant exclusion feedback form identifying which (or both) of the exclusion criteria they met.
- The participant is talked through the participant exclusion feedback form and provided with the chance to ask questions.
- They are thanked for their time, and if they are happy to leave, then they are walked to the door.
- Their personal data is deleted in compliance with GDPR.

[figure not shown]
Testing day 1

Participants arrive at WARU on their pre-organised day and time after a 12 hour fast for a venous blood draw (3 tubes), followed by tea and toast. They are asked to complete an EQ-5D (5L) questionnaire. Their height and weight, waist, and hip circumference are measured. They are then free to leave, unless they have chosen to combine testing day 1 and 2 together, in which case they are guided to the P5 building where the activities outlined under testing day 2 commence.

Testing day 2 (can be combined with day 1 if needed)

If participants opt not to combine testing days 1 and 2 together, then they are met at the main reception and guided to the P5 building, where they are encouraged to go to the toilet prior to testing. They are then taken to P4, where the EEG laboratory is located. They shall then undergo their first EEG and cognitive assessment. They are first asked to participate in an eyes open/closed task for measurements of their EEG resting state. Following this, three cognitive tasks (the Stroop task, the Go/No-go task, and the Flanker task) are digitally completed in a computer program called E-Prime. Practice rounds are provided for each task, with the researcher present, to allow for any questions before each experiment begins. After each task, the EEG program is stopped, and a new data file is created, before recording for the following task takes place. This provides an opportunity in between tasks for a sip of water, or a toilet break, if necessary, although the EEG cap must remain in place, and the nearest accessible toilets are in P5. Altogether, the tasks shall take approximately 60-70 minutes to complete, with an additional 45 minutes allocated for the application of the EEG cap. Participants are encouraged to bring their own bottled drinks, and snacks are made available. They are also granted access to the 'break out' room on the second floor of P5, prior to and following their participation, where there are chairs and tea/coffee machines available. Following their participation, participants are re-directed back to WARU for the collection of their capsules. Participants are reminded before taking part that they will not receive any scores post EEG testing, indicating how well they performed, but that the overall general findings of the study can be made available to them, following the end of the study, by contacting [contact].

Testing day 3

After the 6-week supplementation period, participants are asked to complete the activities that they undertook during testing day 2. A staff member is told to meet the participant in the P5 lobby to walk them over to P4. This is the final assessment of EEG and cognitive testing. If participants decide to combine testing days 3 and 4 together, then a staff member is made available to walk participants down to WARU.

Note: All participants are encouraged to try to combine testing days 3 and 4 together (if possible), to ensure that cognitive testing and the venous blood draw occur within the same 48-hour window to when the last capsules of the 6-week trial are taken.

Testing day 4 (can be combined with day 3 if needed)

Within 48 hours after testing day 3, still following the supplementation regime, participants are invited to WARU after a 12 hour fast for their final venous blood draw (3 tubes), followed by tea and toast. They are then asked to digitally complete the EQ-5D (5L) and MMSE questionnaires. Their height and weight, waist, and hip circumference measurements are taken. There is an optional feedback questionnaire at the end.

6) Participant Risks

The supplements have already been tested for any adverse effects in a human cohort, however if any negative effects occur, participants are asked to refrain from continuing in the study.

EEG is non-invasive, however placing the EEG electrodes along the scalp can be time consuming (approximately 45 minutes), and participants are required to sit relatively still during the application and testing process (the application and testing process combined take approximately 2 hours). The application of the EEG cap requires EEG gel (saline solution) to be applied to the scalp, which makes hair messy upon removal of the cap. Participants are informed that towels will be placed along their shoulders to avoid the solution meeting their clothes, and these towels (in addition to paper towels) are provided to remove any excess gel from their hair. Participants are reminded that hair washing facilities are available in P5 for them to use, but that this would require a short walk from P4 back to P5. Therefore, participants are advised to bring a hat to cover their head for their own comfort. Participants are also reminded that venous blood draws can also cause localised soreness, stress, and dizziness.

7) Benefits to participant

There is no financial gain for participants if they decide to join this study. They will allow us to gain important insight into the PoZibio™ supplement to improve cognitive performance in healthy volunteers, which may be applied to other cohorts such as those suffering from vascular dementia and Alzheimer's disease.

8) Privacy/confidentiality

GDPR: For the data the Welsh Government requires, Welsh Government is the data controller and Aberystwyth University (WARU) is the data processor. For any other data, including sensitive personal data, the data controller and the data processor is Aberystwyth University (WARU).

Participants are informed that only the researchers involved with the study will be able to look at the information they provide. Specific details and personal identifiers will only be available to the researchers. At the end of the study, any information relating to participants will be made pseudonymous (coded without their name associated). Participants will not be identifiable in any publication that may arise from this research. Electronic files will be kept in a logical manner and will always be kept grouped within specific folders and password-protected.

protected. Files are backed up and all data storage is using the AU network. Once the raw data has been extracted from a paper version onto a computer, the paper will be destroyed via a paper shredder or in confidential waste bags to ensure the participant's confidentiality. There may be times when keeping paper forms are necessary (consent forms), but in this case the paper versions will be kept in a locked filing cabinet. All files that are stored on the WARU share drive will always be protected with a secure password. Setting passwords will automatically encrypt the document and will not allow any unauthorised access to the data. The Gatekeeper of the passwords delivers the passwords by encrypted emails. All biofluids are stored in a locked freezer. Key is kept by the gatekeeper. EEG recordings will be stored on a password protected PC in the EEG lab. Due to the nature of the datafiles and the location of the software, it is not possible to store these files in a password protected folder on OneDrive. The lab PC is password-protected, files are stored under random codes and the PC itself is not connected to any network or the internet. EEG recordings will be removed (by deletion) from the lab PC after five years but may be removed sooner due to disk space issues. Only authorised staff members have access to the EEG lab, and the key for the storage cupboard affiliated with the EEG lab is stored within the locked EEG lab.

9) Safety Monitoring

- Participant:

If a participant, or a member of their family/household become unwell during the study, then they are pre-warned to alert a member of the research team immediately using the contact information they have been provided. Participation in the study will be suspended immediately until further discussion with the research team has taken place. If they become unwell at any point and need medical assistance, they are advised to contact 111 and seek advice from the NHS health sector or their doctor's surgery. We have a duty of care towards them and can help monitor their health remotely over 14 days and will help in any way we can.

- Data:

As above

10) Data analysis and statistics

EEG data analysis will be conducted at Aberystwyth University. Chemical composition using metabolomics will be conducted at AberInnovation and Aberystwyth University, and the quantification of short chain fatty acids as well as clinical biochemistry (Chem21 to include

Athrofa y Gwyddorau Biolegol, Amgylcheddol a Gwledig
Institute of Biological, Environmental and Rural Sciences

lipid panel tests) will be analysed
conducted by the Aberystwyth University researchers.

at Bronglais hospital. Statistics will be

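### Six of the 12 secondary entries are before-after changes in the pozibio arm alone, so a shift common to both arms could meet a listed outcome with no product effect

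*Protocol*

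**What the plan says.** Protocol section 5.3 fixes the design: "This is a randomised, placebo controlled, parallel study". Section 2 plans 30 participants over 6 weeks, and gives no allocation ratio.

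Section 5.1.2 has 12 secondary entries, made up of six measures entered twice. The measures are C-reactive protein (CRP), kidney function tests, total cholesterol, total triglyceride, liver function tests and plasma short chain fatty acids.

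- One entry of each pair compares pozibio at 6 weeks with its own baseline. Examples are "Reduced C-reactive protein from baseline at 6 weeks after pozibio", "Reduced Kidney function tests from baseline at 6 weeks after pozibio", "Reduced total Cholesterol from baseline at 6 weeks after pozibio" and "Increased concentration of total short chain fatty acids after the pozibio at 6 weeks compared with the baseline".
- The other compares the arms at 6 weeks, for example "Reduced C-reactive protein at 6 weeks after pozibio when compared with placebo after 6 weeks".

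Nothing in the protocol ranks the placebo comparison above the baseline one or calls the baseline entries descriptive. Section 10 says where the analyses will be done and who will do the statistics, and no more.

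**The concern.** In a parallel placebo-controlled trial, only the contrast between randomised arms can attribute a change to the product. Each before-after entry is directional (a reduction, or for short chain fatty acids an increase) and is judged without looking at the placebo arm. Anything that moves both arms alike over 6 weeks counts towards it: a seasonal change, altered diet while taking part, or assay drift between the two sampling days.

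Each measure also has two listed ways to show the stated direction. A significant fall from baseline beside a null placebo comparison could be presented as a met secondary outcome. That would be a true statement about the listed outcome and would say nothing about the product.

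**Working it through.** **Count.** Six measures × 2 entries = 12, of which 6 (50%) are within-arm only. The kidney entry names four analytes and the liver entry six, so the six measures span 1 + 4 + 1 + 1 + 6 + 1 = 14 quantities. Section 5.1.1 has the same pattern. Its eight measures (Stroop, Go/No-go and Flanker performance, event-related potentials in each of those three tasks, alpha and delta activity, EQ-5D) are entered twice, so 8 of 16 primary entries are within-arm only.

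**Plan's own figure.** There is none to reproduce. The protocol gives no alpha, power, SD, effect size or drift.

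**Inputs for the illustration.** Only the total of 30 comes from the documents. The rest is assumed:

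- 15 per arm (1:1) and no product effect.
- Two-sided 5% tests, counted only in the stated direction.
- A single continuous, normally distributed marker with baseline to week-6 correlation ρ = 0.7.
- The same drift δ in both arms, in that direction, in units of the marker's SD.

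**Within-arm entry.** The SD of the change is √(2(1 − ρ)), which is √0.6 = 0.775 at ρ = 0.7. The paired t statistic has 14 degrees of freedom and noncentrality δ√15 / √(2(1 − ρ)).

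- δ = 0.2: 0.2 × 3.873 / 0.775 = 1.0, so significant in the stated direction in 15% of trials.
- δ = 0.5: 0.5 × 3.873 / 0.775 = 2.5, so 64%.

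**Between-arm entry.** The drift cancels from the difference, so the rate stays at about 2.5% for every δ.

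**Either entry counted.** With no drift, two independent tests would give 1 − 0.975² = 4.9%. The tests share the pozibio arm, and simulation (40,000 trials per scenario) gives 4.8% when arms are compared on week-6 values and about 4% when they are compared on change. With drift, ρ = 0.7 and week-6 values compared between arms:

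| Common drift (SD) | Between arms only | Either entry |
|---|---|---|
| 0 | 2.5% | about 5% |
| 0.1 | 2.5% | 9% |
| 0.2 | 2.5% | 17% |
| 0.3 | 2.5% | 30% |
| 0.5 | 2.5% | 64% |

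**Sensitivity to correlation at δ = 0.5.** The SD of the change is 1.0 at ρ = 0.5 and 0.447 at ρ = 0.9. The noncentralities are 1.94 and 4.33, and the either-entry rates are 44% and 98%.

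**Cross-check on another scale.** With drift in SDs of the change score, and significance counted in either direction, the within-arm test alone is significant in 11%, 19%, 44% and 82% of trials at 0.2, 0.3, 0.5 and 0.8 SD. The between-arm test stays at about 5%. At ρ = 0.7, 0.5 marker SD equals 0.5 / 0.775 = 0.65 change-score SD, so the two sets of figures agree.

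**The case against.** The strongest reply is that the valid contrast is already there. All six measures have an explicit placebo-controlled entry, the protocol states no rule that either entry suffices, and a statistical analysis plan that is not shown may treat the before-after entries as descriptive. That stands, and it limits the claim. A reader might infer that common drift will be reported as a product effect. The documents do not say so; they only leave it open. The reply does not remove the point, because section 5.1.2 itself gives an uncontrolled change the rank of a secondary outcome.

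A reader might also cite regression to the mean. The documents do not support it here: no eligibility criterion in section 5.2 selects on any of these blood measures. Season, diet and assay drift remain possible, but the protocol gives no information on their size.

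The percentages depend on assumed inputs, and the drift must run in the stated direction. With little or no drift the cost is modest, about 5% to 9% per marker up to 0.1 SD. The rates apply to a single marker and do not describe the kidney and liver panels as wholes.

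Finally, the primary list has the same form. There the issue matters more, because repeating the computer tasks invites practice gains in both arms. That is a reason to correct both lists, since correcting only the primary list would leave these six entries in place.

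**Conclusion.** The point holds as a fault in how the outcomes are defined. Half of the secondary entries cannot show a product effect, yet they rank equally with the entries that can. The count and the equal ranking are read directly from section 5.1.2 and need no assumption. What follows is that a common shift could satisfy a listed outcome; the protocol does not say that it would be reported as success.

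The size is illustrative. With 15 per arm and correlation 0.7, allowing either entry roughly doubles the per-marker false-success rate even without drift (about 2.5% to 5%), and takes it to 17% at a favourable common drift of 0.2 SD. The 0.5 SD figure, 64%, moves between 44% and 98% as correlation goes from 0.5 to 0.9, so it should not be quoted without its assumptions. The point should be addressed, but the controlled comparison is not missing.

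**What to change.** In section 5.1.2, keep one inferential entry per measure: the pozibio minus placebo difference at 6 weeks, adjusted for the baseline value already collected. For the kidney and liver panels, state this per analyte, because a single adjusted difference is not defined for a panel. Reword the six before-after entries as descriptive within-arm changes, shown for both arms without a test. Apply the same correction to the 8 of 16 primary entries in section 5.1.1 that have this form.

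The cost is the rewording of six secondary and eight primary lines, and naming the analytes in the two panel entries. No new data, visits or participants are needed.

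### Section 5.1.2 gives one direction, a reduction, to the whole kidney and liver panels, which is wrong for albumin, sodium and potassium

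*Protocol*

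**What the plan says.** Section 5.1.2 of the protocol defines the kidney outcome as "Kidney function tests including sodium/potassium/creatinine/urea". Its two time frames are "Reduced Kidney function tests from baseline at 6 weeks after pozibio" and "Reduced Kidney function tests at 6 weeks after pozibio when compared with placebo after 6 weeks".

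The liver outcome lists AST, ALT and ALP, then "Gamma-glutamyltransferase (GGT), Prothrombin time (PT), Albumin". Its two time frames are "Reduced Liver function test from baseline at 6 weeks after pozibio" and "Reduced Liver function test results at 6 weeks after pozibio when compared with placebo after 6 weeks".

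No analyte in either panel has a direction of its own. Section 5.1.2 mentions no reference range and no criterion of staying within normal limits.

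**The concern.** The bracketed time-frame field in sections 5.1.1 and 5.1.2 does more than give a time point. It also carries the result the investigators hope to see. When one such direction is given to a panel of unlike analytes, it can point the wrong way for some of them.

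What is at stake is how results are labelled and read. A lower albumin, sodium or potassium on pozibio should prompt the question whether something is wrong. Under the current wording it agrees with a listed secondary outcome.

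**Working it through.** No arithmetic decides this point. It turns on three readings of the text.

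**1. Does the field state a hoped-for direction?** The word 'desired' does not appear, so this has to be inferred from the neighbouring entries.

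| Outcome | Direction in the bracket | Sense |
|---|---|---|
| Stroop and Flanker (5.1.1) | improved | benefit |
| Go/No-go (5.1.1) | improved, fewer errors | benefit |
| C-reactive protein (5.1.2) | "Reduced C-reactive protein from baseline at 6 weeks after pozibio" | benefit; described as an inflammation marker |
| Plasma short chain fatty acids (5.1.2) | increased | hoped-for rise |
| Kidney and liver panels (5.1.2) | reduced | same field, same form |

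The authors vary the direction with the outcome, and elsewhere it is the hoped-for one. A neutral meaning for the kidney and liver entries alone would break that pattern.

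**2. Does the direction suit each named analyte?** The population is healthy (section 2), so there is no raised starting level to bring down. The classification below is general clinical knowledge, not something the protocol supplies.

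| Analyte | Is a fall a suitable one-way target? |
|---|---|
| Albumin | No. A fall suggests poorer synthetic function or nutrition. |
| Sodium, potassium | No. Both are regulated within a range; a fall is no benefit and can be harmful. |
| AST, ALT, GGT | Defensible; a lower value is usually favourable or neutral. |
| ALP, prothrombin time, creatinine, urea | A lower value is usually favourable or neutral, but when values are already in range a fall is not clearly a benefit. |

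The liver panel also conflicts with itself. Better synthetic function would show as a shorter prothrombin time and a higher albumin, so one word cannot describe both.

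**3. How far does the problem extend?** The entries in 5.1.2 that state a reduction are C-reactive protein 2, kidney 2, total cholesterol 2, total triglyceride 2 and liver 2: 2 + 2 + 2 + 2 + 2 = 10. The panel-wide ones are kidney 2 + liver 2 = 4. The other 10 − 4 = 6 each name a single measure, so the mixed-panel problem does not arise there. Nothing elsewhere in the protocol qualifies the direction for the four panel entries.

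**The case against.** The strongest reply is that this is loose wording in a field labelled as a time frame. The protocol attaches no test, success rule or decision to these outcomes, and section 10 says only where and by whom the analyses are done. Clinical biochemistry is analysed at a hospital, and someone may well recognise a low sodium for what it is. This limits the consequence and stands. It does not make the stated direction right, and the direction is text the protocol itself fixes, not detail left to an analysis plan.

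Three stronger readings are tempting, and the document does not support them.

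- *Three of the ten named analytes are wrong, so 30% of these results are compromised.* The three failures are clear, but the fraction depends on how the other seven are judged. Participants are healthy, and serious conditions needing daily long-term medication are excluded. In such people a lower in-range creatinine, urea, ALP or prothrombin time is not clearly a benefit; lower creatinine in older adults can reflect less muscle. A strict test would fail more than three. The kidney list is also open-ended. The count is therefore no measure of impact.
- *The trial would declare success on a fall in albumin or sodium.* No rule in the protocol leads to that, and whether such a fall would be reported as favourable is conjecture.
- *The protocol leaves abnormal laboratory results without follow-up.* That is a separate safety-reporting matter. It depends on participant material that is not available here, and it does not follow from the direction error.

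**Conclusion.** The point holds as a wrong stated direction in four secondary time frames. It is clearest for albumin, and it also holds for sodium and potassium. It rests on two assumptions: that the bracketed direction is the hoped-for result, which the parallel entries support, and on ordinary clinical understanding of the three analytes. No laboratory value or outside figure is needed.

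The impact is minor. The outcomes are secondary, they have no success rule, and the primary question is unaffected. The correction is worth making because the text as it stands would let an adverse change agree with a stated outcome.

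**What to change.** In the four kidney and liver time frames of section 5.1.2, replace the reduction with: *change from baseline to 6 weeks in each analyte, compared between pozibio and placebo, two-sided, read as safety measures against the hospital laboratory's reference range*. The two entries for each panel would then say the same thing and can be merged.

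If the sponsor wants a directional hypothesis, state it only for named analytes such as the liver enzymes, and never for albumin, sodium or potassium. It would not be enough to keep a reduction as the target for the other seven analytes and exempt these three, since healthy participants do not need a fall in those either.

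The cost is protocol wording only. Blood is already drawn at baseline and at the end of supplementation (section 5.3, testing days 1 and 4), so no visit or sample is added.
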